## **5.3. Method of Assignment to Treatment**

After the informed consent form (ICF) is signed and dated, a patient is considered to be “entered” into the study and will be assigned a patient number. Patients who meet all criteria for enrollment will be randomized to double-blind treatment at Visit 2. Assignment to treatment groups will be determined by a computer generated random sequence using an IVRS. The IVRS will be used to assign investigational product packages containing double-blind investigational product to each patient during Study Period II, and open-label investigational product during Study Period III. Site personnel will confirm that they have located the correct investigational product packages by entering a confirmation number found on the investigational product packages into the IVRS.

Individuals who do not meet certain criteria for participation in this study (screen failure) may be re-screened. Individuals may be re-screened one time. The interval between screening and re-screening should be at least 3 weeks. When re-screening is performed, the individual must sign a new ICF and will be assigned a new identification number.

To achieve between-group comparability for site factor, the randomization will be stratified by site.

## 6. A Priori Statistical Methods

### 6.1. Statistical and Analytical Plans

The protocol for this study was approved on 25 October 2010. The protocol amendment (a) was approved on 13 July 2011. The protocol amendment (b) was approved on 24 April 2013. The version 2 of SAP will supersede the statistical plans described in the protocol amendment (b). Section 6.1 addresses the statistical analyses planned before unblinding.

#### 6.1.1. Analysis Populations

All data presentations will be based the intent-to-treat (ITT) population, which includes all randomized patients.

#### 6.1.2. General Considerations

Efficacy and safety analyses will be done on an intent-to-treat (ITT) basis unless otherwise specified. An intent-to-treat analysis is an analysis of data by the groups to which patients are assigned by random allocation, even if the patient does not take the assigned treatment, does not receive the correct treatment, or otherwise does not follow the protocol.

All efficacy and safety analyses of continuous measures will include randomized patients with both a baseline and at least one post-baseline value for the variable being analyzed. For efficacy and continuous safety variables, baseline is defined as the last measurement taken at, or prior to the visit where the study period begins; endpoint is defined as the last non-missing measurement for the study period of interest. Table HMGW 6.1 provides baseline and post-baseline definitions for all variables.

Statistical analyses will be carried out for Study Period II, III, and IV (SP II-IV). All tests of hypotheses will be evaluated based on a two-sided significance level of 0.05 unless otherwise specified. No adjustments for multiple comparisons will be made.

For SP II, a patient's treatment group will be determined by the treatment to which the patient is randomized: either duloxetine (DLX) or placebo (PLA).

For SP III, the following treatment groups will be determined by the randomized treatment at SP II and extension phase treatment at SP III:

PLA/DLX: patients who are randomized to placebo at SP II and who enter SP III and take duloxetine.

DLX/DLX: patients who are randomized to duloxetine at SP II and who enter SP III and take duloxetine.

No statistical comparisons will be conducted to compare the two treatment groups PLA/DLX and DLX/DLX during SP III unless otherwise noted. For continuous measures, when appropriate, within treatment testing of change from baseline for selected safety and efficacy measures will be conducted for SP III.

For SP II/III, one treatment group will be determined by the randomized treatment at SP II:

DLX: patients who are randomized to duloxetine at SPII, including patients who may have discontinued early at SPII or who enter SPIII.

For SP IV, a patient's treatment group assignment will be based on the last treatment received before entering Study Period IV and the treatment received during SP IV: PLA\_PLA, DLX30\_PLA, or DLX60\_DLX30. SP IV is not required for patients who discontinue the study during SP III on the duloxetine dose of 30 mg (Visit 9-15), however it would be allowed based on investigator decision.

Table HMGW.6.1 below presents baseline and post-baseline period definitions for each study period and for each safety and efficacy analysis.

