### 5.1. Summary of Study Design

Study F1J-MC-HMGW (HMGW) is a Phase 3b, multicenter, randomized clinical trial of duloxetine versus placebo for the treatment of JPFS in adolescents. The study design includes 4 study periods. Following Study Period I (screening phase), eligible patients enter Study Period II, the acute 13-week parallel, randomized, double-blind, placebo-controlled treatment period of duloxetine 30/60 mg QD. Upon completion of the 13-week double-blind period, patients enter Study Period III, a 26-week, open-label extension phase of duloxetine 30/60 mg QD. A 1-week drug taper period (Study Period IV) is required for all patients who discontinue for any reason between Visit 4 to Visit 8 during Study Period II, or who complete/discontinue Study Period III on duloxetine 60 mg QD.

Figure HMGW.5.1 illustrates the study design.

Abbreviations: DB = double-blind; DLX = duloxetine; OL = open-label; QD = once-daily

a After Visit 3, patients increased to 60 mg duloxetine can have their dose decreased 1 time, at a scheduled or unscheduled Visit. Once 60 mg dose is decreased to 30 mg, it cannot be increased again during Study Period II.

b At Visits 4 through 8, patients randomized to placebo or DLX 30 mg who discontinue prior to entering the open-label extension treatment period (Study Period III) will receive placebo in the drug taper period.

c At Visits 9 through 14 in Study Period III, dose increases are permitted at scheduled visits (to a maximum dose of 60 mg QD) and dose decreases are permitted at scheduled or unscheduled visits (to a minimum dose of 30 mg QD).

d Patients who complete/discontinue Study Period III on DLX 30 mg do not need to enter the drug taper period.

**Figure HMGW.5.1** Illustration of study design for Protocol F1J-MC-HMGW.

Study Period I is a screening period of approximately 1 week in duration, but not more than 30 days, during which patients will be screened for study eligibility.

Study Period II is a 13-week, acute treatment period. During Study Period II, at Visit 2, patients who meet all study criteria for enrollment will be randomly assigned in a 1:1 ratio to duloxetine or placebo by a computer-generated random sequence using an interactive voice response system (IVRS). All patients will receive investigational product (IP) beginning at Visit 2 and will be instructed to start taking their IP the morning after Visit 2.

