**Table HMGW.6.1 Patient Population with Baseline and Post-baseline Definitions by Study Period and Type of Analysis**

Study Period / Analysis	Patient Population	Baseline Definition	Post-baseline Definition
Acute Phase			
Efficacy	Patients with a baseline and at least one post-baseline observation	Last of Visits 1-2	All Visits 3-8
TEAEs	All randomized patients	All Visits 1-2	All Visits 2.01-8
SAE and DCAE	All randomized patients	NA	All Visits 2.01-8
C-SSRS categorical analyses	All randomized patients	Lifetime baseline: All Visits 1-2 Lead-in baseline: Visit 2	All Visits 2.01-8
Treatment Emergent Abnormal Labs	Patients with normal laboratory values at all nonmissing baseline visits (with respect to direction being analyzed) and who have at least one post-baseline observation	All of Visits 1-2	All Visits 2.01-8
Treatment emergent low blood pressure	Patients with normal values at all nonmissing baseline visits (with respect to direction being analyzed) and who have at least one post-baseline observation. See Table HMGW.6.4 for normal limits of blood pressure.	Minimum value from Visits 1-2	All Visits 2.01-8
PCS in vital signs, weight, sustained blood pressure analyses	Vital signs: Patients with normal values at all nonmissing baseline visits (with respect to direction being analyzed) and who have at least one post-baseline observation. See Table HMGW.6.4 for normal limits of vital signs. Weight:	Low: Minimum value from Visits 1-2 High: Maximum value from Visits 1-2	All Visits 2.01-8

	Patients with non-missing baseline and at least one post-baseline value.		
Treatment-emergent changes in ECG intervals and heart rate	Patients with normal values at all nonmissing baseline visits (with respect to direction being analyzed) and who have at least one post-baseline observation. See Table HMGW.6.8 for normal limits of ECG.	Low: Minimum value from Visits 1-2 High: Maximum value from Visits 1-2	All Visits 2.01-8
Continuous Safety measures	Patients with a baseline and at least one post-baseline observation	Last of Visits 1-2	All Visits 3-8
Extension Phase			
Efficacy	Patients with a baseline and at least one post-baseline observation	Last of Visits 3-8	All Visits 9-15
TEAEs	All randomized patients entering extension phase	Maximum severity between $7 \leq \text{Visit} \leq 8$	All Visits 8.01-15
SAE and DCAE	All randomized patients entering extension phase	NA	All Visits 8.01-15

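### In Study Period II, adverse events, SAEs and discontinuations due to AEs are analysed only in all randomized patients by randomized arm, with no dosed-patient analysis, so undosed or mis-dosed patients could dilute the harm comparison

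*SAP*

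**What the plan says.** Section 6.1.1 bases every data presentation on "the intent-to-treat (ITT) population, which includes all randomized patients". Section 6.1.2 extends this to safety: "Efficacy and safety analyses will be done on an intent-to-treat (ITT) basis unless otherwise specified". It keeps the randomized group "even if the patient does not take the assigned treatment, does not receive the correct treatment, or otherwise does not follow the protocol", and on grouping it states: "For SP II, a patient's treatment group will be determined by the treatment to which the patient is randomized".

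In Table HMGW.6.1, the acute-phase TEAE row and the SAE and DCAE row both give the population as "All randomized patients", without a dosing condition. The combined SP II/III duloxetine group is also defined by randomization (6.1.2). Sections 6.1.14.1 and 6.1.2 together use that group for the SP II/III TEAE summary and for the Kaplan-Meier curves of time to common TEAEs and to discontinuation due to an AE.

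Other safety analyses have narrower populations:

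- Continuous measures "will include randomized patients with both a baseline and at least one post-baseline value for the variable being analyzed".
- Laboratory, vital sign and ECG categories need at least one post-baseline observation.
- The C-SSRS row of the table carries the all-randomized label, but section 6.1.14.5 limits the analysis to patients with a post-baseline assessment.

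**The concern.** Study Period II is the only placebo-controlled safety comparison in these adolescents; Study Period III is open-label and its safety data are descriptive. Analysing everyone as randomized is the cautious choice for a superiority claim on efficacy. For harms it works the other way. A duloxetine patient who never took a capsule adds to the denominator but cannot have a drug reaction. A placebo patient who received duloxetine may have a reaction that is counted under placebo. Both move the comparison towards no difference.

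Never-dosed patients are possible by design, because patients "will be instructed to start taking their IP the morning after Visit 2". Two other rules show that the plan does not provide for them:

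- Section 6.1.14.1 makes an event treatment-emergent when its onset is after Visit 2, not after the first dose. A background event in a never-dosed patient is therefore labelled treatment-emergent.
- Section 6.1.10 summarises exposure for all ITT patients from the first dose date on the eCRF. Only a missing last dose date is imputed, so exposure is undefined for a patient who never dosed.

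**Working it through.** The SAP has no figure of its own to reproduce here: it states no number of undosed or mis-dosed patients and no adverse event rates. What follows is arithmetic on stated assumptions.

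**Input from the SAP.** Section 5.2 plans about 184 patients at 1:1, so n = 184/2 = 92 per arm.

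**Assumed inputs.**
- True event rates pD on duloxetine and pP on placebo.
- u: duloxetine patients never dosed, having events at rate pP.
- c: patients in each arm who received the other arm's drug (c swapped pairs).

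**Formula.**
- Duloxetine arm as randomized: pD − [(u + c)/n] × (pD − pP)
- Placebo arm as randomized: pP + (c/n) × (pD − pP)
- Difference as randomized: (pD − pP) × [1 − (u + 2c)/n]

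Each undosed duloxetine patient removes 1/92 = 1.1% of the difference. Each swapped pair removes 2/92 = 2.2%.

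| Assumed rates | u | c | Factor | Difference as randomized |
|---|---|---|---|---|
| 20% vs 10% | 0 | 0 | 92/92 | 10.0 points |
| 20% vs 10% | 1 | 0 | 91/92 | 9.9 |
| 20% vs 10% | 5 | 0 | 87/92 | 9.5 |
| 20% vs 10% | 9 | 0 | 83/92 | 9.0 |
| 20% vs 10% | 0 | 1 | 90/92 | 9.8 |
| 20% vs 10% | 5 | 2 | 83/92 | 9.0 |
| 30% vs 15% | 1 | 0 | 91/92 | 14.8 |
| 30% vs 15% | 5 | 0 | 87/92 | 14.2 |
| 30% vs 15% | 9 | 0 | 83/92 | 13.5 |

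At 20% vs 10%, going from 0 to 9 undosed duloxetine patients lowers the approximate power of that comparison from 0.48 to 0.41.

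**Sensitivity to the background rate.** Take a duloxetine rate of 60% and 5 undosed patients. If all 5 are event-free, the reported rate is 0.60 × 87/92 = 56.7%, which is the worst case. If they have events at an assumed 40% background rate, it is 0.60 × 87/92 + 0.40 × 5/92 = 58.9%, a shift of 1.1 points instead of 3.3.

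**Rare events.** Suppose 3 vs 0 events by drug received, with one of the three in a placebo-assigned patient who was given duloxetine. By randomized arm this is reported as 2 vs 1. The total does not change; one event moves between columns.

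**The case against.** The strongest reply is that the rule is stated openly, applied consistently in Study Period II and contradicts nothing in the SAP. It also preserves the randomized comparison, which regrouping by drug received gives up. Wrong packs are guarded against: section 5.3 has sites confirm each package number in the IVRS. The planned exposure summaries, compliance listing and AE listings would help to reveal undosed patients. All of this stands, and it is why the point is minor. It does not supply a harm table restricted to dosed patients.

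Three stronger readings are tempting, and the SAP does not support them:

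- A reader might infer that all safety data are analysed in all randomized patients. That is true only of TEAEs, SAEs and DCAEs. Laboratory, vital sign, ECG, continuous safety and C-SSRS analyses need post-baseline data. That is not a dosing condition, but it removes most never-dosed patients. What remains is the wrong-drug part, because these analyses are still grouped as randomized in Study Period II.
- A reader might infer that only the placebo-controlled period ignores the treatment taken. The SP II/III group is also set by randomization. The Study Period III groups do require duloxetine to be taken, but everyone is on duloxetine there, so this is no precedent for regrouping between arms. Only the Study Period IV grouping, which "will be based on the last treatment received before entering Study Period IV and the treatment received during SP IV", is truly by treatment received.
- A reader might infer that duloxetine harm rates are in fact diluted. The SAP gives no count of undosed or mis-dosed patients, so dilution is a possibility and not a finding.

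**Conclusion.** The point holds in limited form, as an inexpensive improvement and not an error that threatens the trial. It covers Study Period II TEAEs, SAEs and DCAEs and the duloxetine SP II/III TEAE summaries and Kaplan-Meier curves.

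Under the assumptions above, a handful of undosed or mis-dosed patients costs roughly 1% to 10% of the difference in relative terms. Common events would barely move. A rare SAE comparison is more exposed, because a single event in the wrong column can change how it reads. The size rests entirely on assumed counts and rates.

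**What to change.** 1. In sections 6.1.1 and 6.1.2 and in the acute-phase TEAE and SAE/DCAE rows of Table HMGW.6.1, define a Study Period II safety set: randomized patients with at least one dose, grouped by treatment received. State in advance how a patient who took both treatments is classified.
2. Use this set for Study Period II TEAEs, SAEs, DCAEs and exposure. Apply the same dosing condition to the duloxetine SP II/III AE summaries and Kaplan-Meier curves in section 6.1.14.1. This also resolves the undefined exposure of never-dosed patients in section 6.1.10.
3. Keep the all-randomized tables as a check.
4. List undosed and mis-dosed patients, with the timing of their events relative to the drug taken, so that an event before a dispensing error is not read as a reaction to the wrong drug.
5. Leave efficacy on all randomized patients.

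The cost is SAP wording and one population flag, built from the first dose date on the eCRF (6.1.10) and the IVRS package records (5.3). The downside is that the main safety comparison is no longer strictly as randomized, and with few cases regrouping can itself shift rare-event counts. The all-randomized check covers this. If everyone is dosed as assigned, the two sets of tables coincide.

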**Table HMGW.6.1 Patient Population with Baseline and Post-baseline Definitions by Study Period and Type of Analysis**

Study Period / Analysis	Patient Population	Baseline Definition	Post-baseline Definition
Acute Phase			
Efficacy	Patients with a baseline and at least one post-baseline observation	Last of Visits 1-2	All Visits 3-8
TEAEs	All randomized patients	All Visits 1-2	All Visits 2.01-8
SAE and DCAE	All randomized patients	NA	All Visits 2.01-8
C-SSRS categorical analyses	All randomized patients	Lifetime baseline: All Visits 1-2 Lead-in baseline: Visit 2	All Visits 2.01-8
Treatment Emergent Abnormal Labs	Patients with normal laboratory values at all nonmissing baseline visits (with respect to direction being analyzed) and who have at least one post-baseline observation	All of Visits 1-2	All Visits 2.01-8
Treatment emergent low blood pressure	Patients with normal values at all nonmissing baseline visits (with respect to direction being analyzed) and who have at least one post-baseline observation. See Table HMGW.6.4 for normal limits of blood pressure.	Minimum value from Visits 1-2	All Visits 2.01-8
PCS in vital signs, weight, sustained blood pressure analyses	Vital signs: Patients with normal values at all nonmissing baseline visits (with respect to direction being analyzed) and who have at least one post-baseline observation. See Table HMGW.6.4 for normal limits of vital signs. Weight:	Low: Minimum value from Visits 1-2 High: Maximum value from Visits 1-2	All Visits 2.01-8

	Patients with non-missing baseline and at least one post-baseline value.		
Treatment-emergent changes in ECG intervals and heart rate	Patients with normal values at all nonmissing baseline visits (with respect to direction being analyzed) and who have at least one post-baseline observation. See Table HMGW.6.8 for normal limits of ECG.	Low: Minimum value from Visits 1-2 High: Maximum value from Visits 1-2	All Visits 2.01-8
Continuous Safety measures	Patients with a baseline and at least one post-baseline observation	Last of Visits 1-2	All Visits 3-8
Extension Phase			
Efficacy	Patients with a baseline and at least one post-baseline observation	Last of Visits 3-8	All Visits 9-15
TEAEs	All randomized patients entering extension phase	Maximum severity between $7 \leq \text{Visit} \leq 8$	All Visits 8.01-15
SAE and DCAE	All randomized patients entering extension phase	NA	All Visits 8.01-15
C-SSRS categorical analyses	All randomized patients entering extension phase.	Lifetime baseline: All Visits 1-8 Lead-in baseline: $7 \leq \text{Visit} \leq 8$	All Visits 8.01-15
Treatment Emergent Abnormal Labs	Patients with normal laboratory values at all nonmissing baseline visits (with respect to direction being analyzed) and who have at least one post-baseline observation	All Visits 2.01-8	All Visits 8.01-15
Treatment emergent low blood pressure	Patients with normal values at all nonmissing baseline visits (with respect to direction being analyzed) and who have at least one post-baseline observation. See Table HMGW.6.4 for normal limits of blood pressure.	Minimum value from Visits 2.01-8	All Visits 8.01-15
PCS in vital signs, weight, sustained blood pressure analyses	Vital signs: Patients with normal values at all nonmissing baseline visits (with respect to direction being analyzed) and who have at least one post-baseline observation. See Table HMGW.6.4 for normal limits of vital signs. Weight: Patients with non-missing baseline and at least one post-baseline value.	Low: Minimum value from Visits 2.01-8 High: Maximum value from Visits 2.01-8	All Visits 8.01-15
Treatment-emergent changes in ECG intervals and heart rate	Patients with normal values at all nonmissing baseline visits (with	Low: Minimum value	All Visits 8.01-15

	respect to direction being analyzed) and who have at least one post-baseline observation. See Table HMGW.6.8 for normal limits of ECG.	from Visits 2.01–8 High: Maximum value from Visits 2.01–8	
Continuous Safety measures	Patients with a baseline and at least one post-baseline observation	Last of Visits 3-8 (for vital sign analysis, another baseline is: Last of Visits 1-2)	All Visits 9-15
Acute and Extension Phase Combined			
Efficacy	Patients with a baseline and at least one post-baseline observation	Last of Visits 1-2	All Visits 3-15
Treatment emergent low blood pressure	Patients with normal values at all nonmissing baseline visits (with respect to direction being analyzed) and who have at least one post-baseline observation. See Table HMGW.6.4 for normal limits of blood pressure.	Minimum value from Visits 1-2	All Visits 2.01-15
PCS in vital signs, weight, sustained blood pressure analyses	Vital signs: Patients with normal values at all nonmissing baseline visits (with respect to direction being analyzed) and who have at least one post-baseline observation. See Table HMGW.6.4 for normal limits of vital signs. Weight: Patients with non-missing baseline and at least one post-baseline value.	Low: Minimum value from Visits 1–2 High: Maximum value from Visits 1–2	All Visits 2.01-15
Treatment-emergent changes in ECG intervals and heart rate	Patients with normal values at all nonmissing baseline visits (with respect to direction being analyzed) and who have at least one post-baseline observation. See Table HMGW.6.8 for normal limits of ECG.	Low: Minimum value from Visits 1–2 High: Maximum value from Visits 1–2	All Visits 2.01-15
Continuous Safety measures	Patients with a baseline and at least one post-baseline observation	Last of Visits 1-2	All Visits 3-15
Taper Phase			
Discontinuation emergent AEs	All randomized patients entering taper phase	Maximum severity at last two visits before entering taper	Visit 301
SAE and DCAE	All randomized patients entering	NA	Visit 301

	taper phase		
C-SSRS categorical analyses	All randomized patients entering taper phase	Lifetime baseline: All visits before entering taper phase (Visits 1-15) Lead-in baseline: Last visit before entering taper phase	Visit 301
Continuous measure in vital signs and weight	All randomized patients entering taper phase	Last scheduled visit before entering taper phase	Visit 301

Note: Visit 2.01 indicates the first unscheduled visit occurring after Visit 2 and prior to Visit 3.

Visit 8.01 indicates the first unscheduled visit occurring after Visit 8 and prior to Visit 9.

Abbreviation: AE = adverse event; C-SSRS = Columbia-Suicide Severity Rating Scale; DCAE = adverse event leading to discontinuation; NA = not applicable; PCS = potentially clinically significant; SAE = serious adverse event; TEAE = treatment-emergent adverse event.

A repeated measures analysis refers to a restricted maximum likelihood (REML)-based, mixed-effects repeated measures (MMRM) analysis using all the longitudinal observations at each post-baseline visit. The model for this analysis will include the fixed categorical effect of treatment, pooled investigative site, visit, and treatment-by-visit interaction, as well as the continuous, fixed covariate of baseline value of the variable being analyzed and baseline value of the variable being analyzed-by-visit interaction. An unstructured covariance structure will be used to model the within-patient errors. And Kenward-Roger approximation (Kenward and Roger, 1997) will be used to estimate denominator degrees of freedom. If the default Newton-Raphson algorithm used by SAS PROC MIXED does not converge, then the Fisher scoring algorithm will be applied.

However, if the model with unstructured covariance structure still fails to converge, the sandwich estimator (Diggle, Liang, and Zeger, 1994; Lu and Mehrotra, 2009) will be used to estimate the standard errors of the fixed effects parameters and the model will be fitted using covariance structures in the following order until convergence is met:

heterogeneous toeplitz	type = toeph
heterogeneous autoregressive (1st order)	type = arh(1)
heterogeneous compound symmetric	type = cs(h)
toeplitz	type = toep
autoregressive (1st order)	type = ar(1)
compound symmetric	type = cs

When the sandwich estimator is used, the Kenward-Roger approximation for denominator degrees of freedom cannot be used. Instead, the denominator degrees of freedom will be partitioned into between-subject and within-subject portions (denoted by DDFM= BETWITHIN in the MODEL statement).

For repeated measures analyses of efficacy and safety variables that are not collected at each post-baseline visit, data may exist at visits where the variable was not scheduled to be collected due to early discontinuation visits. Data collected at scheduled visits and early discontinuation visits will be used in the analysis. In these situations, the data from the early discontinuation visit will be carried forward to the next regularly scheduled collection visit for the repeated measures analysis. Significance tests will be based on least-squares means (LSMean) and Type III sum-of-squares, using a two-sided  $\alpha=0.05$ . Analyses will be implemented using SAS® PROC MIXED.

The repeated measures analysis for categorical variables will use a categorical, pseudo-likelihood-based repeated measures (MMRM-CAT) approach. The model will include the fixed, categorical effect of treatment, pooled investigative site, visit, and treatment-by-visit interaction, as well as the continuous, fixed covariate of baseline value of the variable being analyzed and baseline value of the variable being analyzed-by-visit interaction. An unstructured covariance structure will be used to model the within-patient errors. The Kenward-Roger approximation will be used to estimate denominator degrees of freedom. If the model does not converge with the default fitting algorithm used by PROC GLIMMIX, the Fishers scoring algorithm will be utilized by the SCORING option in SAS. If the model still fails to converge, the model will be fitted using covariance matrices in the following order specified by a decreasing number of covariance parameters until convergence is met: heterogeneous toeplitz, heterogeneous autoregressive (1st order), heterogeneous compound symmetric, toeplitz, autoregressive (1st order), compound symmetry. For models where the unstructured covariance matrix is not utilized, the sandwich estimator (Diggle, Liang, and Zeger 1994) will be used to estimate the standard errors of the fixed effects parameters. The sandwich estimator is utilized by the EMPIRICAL option in SAS. When the sandwich estimator is utilized, the Kenward-Roger approximation for denominator degrees of freedom cannot be used. Instead, the denominator degrees of freedom will be partitioned into between-subject and within-subject portions by the DDFM=BETWITHIN option in SAS. This analysis will be implemented using SAS® PROC GLIMMIX.

Unless otherwise specified, when an analysis of variance (ANOVA) model is used to analyze a continuous efficacy variable, the model will contain the main effects of treatment and pooled investigative site. The significance of treatment-by-pooled investigative site interaction will be evaluated in a separate model, when appropriate. Similar logic is applied to an analysis of covariance (ANCOVA) model, which in general, refers to the ANOVA model with baseline values added as covariates. Type III sum-of-squares for the LSMean will be used for the statistical comparison of main effects using ANOVA or ANCOVA. Statistical inference for ANOVA or ANCOVA interaction terms will be based on type II sum-of-squares for the LSMean.

The same MMRM, ANOVA and ANCOVA models excluding treatment effect will be used to present data for Study Period III, where appropriate.

Unless otherwise specified, for all analyses using the last-observation-carried forward (LOCF) approach in Study Period II, endpoint is defined as the last nonmissing observation obtained from Visit 3 through Visit 8; for the analyses using LOCF in Study Period III, endpoint is defined as the last nonmissing observation from Visit 9 through Visit 15.

In the analyses of some efficacy variables for Study Period II, the baseline-observation-carried-forward (BOCF) approach is considered. The BOCF endpoint is defined as follows:

For randomized patients who complete the treatment period (that is, complete the scheduled Visit 8) and have last nonmissing value at Visit 8, the BOCF endpoint is defined as the last nonmissing observation, for randomized patients who discontinue early (that is, do not complete the scheduled Visit 8) but with at least one non-missing baseline value, the BOCF endpoint is defined as the baseline value.

Categorical comparisons between treatment groups will be performed using Cochran-Mantel-Haenszel (CMH) test controlling for pooled investigative site and Fisher's exact test for Study Period II, when appropriate. For the categorical data, the number and percentage of patients for the categorical variables will be presented for Study Period III.

Where appropriate, variables will be summarized descriptively (frequency and percent will be summarized for categorical variables; number of patients with a non-missing observation, mean, SD, median, minimum, and maximum will be summarized for continuous variables) by study visit.

For those data summaries accompanied by individual patient data listings, data will be sorted by investigator ID, patient ID, and visit or event number if it is available.

Changes made to the data analysis methods will not necessarily require a protocol amendment and will be described in an updated SAP and reflected in the final report.

Statistical analysis of this study will be the responsibility of Eli Lilly and Company or designee. SAS® software will be used to perform most or all statistical analyses.

